- The infusion line can connect to the infusion canula without the need to remove its sealing cap. This reduces the amount of surgical movements and allows better surgical flexibility when the infusion needs to be switched to another instrument cannula during surgery.
- The infusion line locks onto the infusion canula, reducing the incidence of a commonly occurring issue that the infusion line disconnects from the cannula during the surgery.

After brought under anesthesia, the patients is draped while the vitrectomy device is being prepared. This involves connecting of all the surgical supplies (see above) and priming of the device. This whole procedure takes 10-20 minutes, depending on the complexity of

the case. The packaging of the surgical supplies was reworked (reduction in the amount of packaging materials) and the infusion giving set has been simplified significantly for the EVA Nexus platform. This should shorten the total surgical time.

Surgical issues and/or (S)AE's that are related to the surgical device will always be observed either during the surgery or during the postoperative visit on day one. Late-onset complications such as proliferative vitreoretinopathy, retinal detachment etc. are considered non-related to the surgical device. Hence, in this study, data acquisition is terminated after the postoperative visit on day one, although the patient will have further postoperative follow-up according the standard of care.

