6. OBJECTIVES

The primary objective and primary parameters are shown in the table below:

The main purpose of this study is to evaluate the intra-operative safety of a new surgical device.
	
Therefore, having no idea of the percentage of patients having complications, we make the hypothesis that minimum 5% of the patients will have complications. In order to make sure that we have at least 10 patients with complications, we plan recruit 250 patients in total in order to get at least 10 complications with EVA Nexus.
 
For this purpose, typical surgical parameters will be recorded during vitrectomy surgery:
 
 • Surgical indication • If combined phaco-surgery is performed: amount of phaco power used • Staining dyes (if used) • Amount of laser coagulates (if used) • Type of tamponade left in the eye: BSS+ liquid, air bubble, air, gas (type + concentration) or silicone oil (type) 
Specific adverse events that may occur during (phaco)vitrectomy will be recorded to assess the surgical safety ¹⁵⁻¹⁸: see list in Appendix A. This AE reporting is already present in the surgical report (KWS-Formasa) used for daily vitrectomy surgery using the DORC EVA device. The occurrence of these AE's during surgeries using the EVA Nexus will be compared to historical data retrieved from surgeries using the DORC EVA platform.
 
Device issues that caused some hindering during the surgery but that do not lead to an (S)AE, such as error messages/warnings that did occur, malfunctioning of supplies that required replacement etc. will be recorded.
 
See Appendix B for a full list, which is already part of our present surgical report (KWS-Formasa). The occurrence of these issues during surgeries using the EVA Nexus will be compared to historical data retrieved from surgeries using the DORC EVA platform.

---	---

The secondary objective and secondary parameters are shown in the table below:

Secondary objective	Secondary parameters
To evaluate the possible reduction of total surgical time.	The time that was required to prepare the EVA Nexus will be recorded (connecting of supplies + priming). During the study period, this time will also be recorded during surgeries performed with the DORC EVA device for comparison.

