To evaluate possible (S)AE that may be related to the use of the surgical platform.	Rarely, adverse events that are related to the surgery may only become visible the day after the surgery. A typical example is a choroidal hemorrhage, which is related to variations in intraocular pressure during the surgery. Hence, standard as in the standard-of care, a postoperative check of the eye at the day after the surgery will be performed to determine the presence of such AE's.
To evaluate the impact of usage of the EVA NEXUS on the surgical parameters used during the procedure	
The surgical parameters include a range of data collected on the following:
 
Aspiration Irrigation / Infusion BSS Usage Vitrectomy Ultrasound Illumination Diathermy Micro-injection Silicone oil injection / extraction Laser

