Appendix A: List of adverse events in eCRF (source document in Formasa)

- **Anterior segment surgery**

Lens surgery complications	 Other  Capsulorhexis zip  Posterior capsule tear  Vitreous prolapse  Iris prolapse  Dropped lens (fragment)
Other lens surgery complication	 
Expand	

- **Posterior segment surgery**

Vitrectomy complications	 Other  None  Iatrogenic retinal tear  Lens touch  Choroidal hematoma  Infusion subretinal  Infusion subchoroidal  Iatrogenic retinal / optic nerve damage  Subretinal hemorrhage  Iris trauma  Retinal incarceration  PFCL subretinal  Oil subchoroidal  Hemorrhage from retinal vessel  Subchoroidal hemorrhage
Vitrectomy complications other	 
Expand	

Appendix B: List of device issues not leading to (S)AE recorded in the Formasa surgical report (and in the eCRF)

Device name	   DORC EVA Nexus
Device preparation time (HH:MM:SS)	   00:04:15
Vitrectomy device problem	  Yes   No 
reset

Infusion bottle empty	  Yes   No 
reset

Infusion bottle empty detected	  Yes   No 
reset

Phaco problem	  Yes   No 
reset

Phaco problem description	 Phaco needle detached from hand piece  Phaco handpiece delivered insufficient power  Error message phaco during priming
Vitrectome problem	  Yes   No 
reset

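### One secondary objective asks about total surgical time, but the only time the plan specifies for it is device preparation time, so it can support a conclusion on preparation only

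*Combined protocol and SAP*

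**What the plan says.** The secondary-objectives table in section 6 has three rows. The first gives the objective "To evaluate the possible reduction of total surgical time". The parameter beside it is "The time that was required to prepare the EVA Nexus will be recorded (connecting of supplies + priming". The comparator follows: "During the study period, this time will also be recorded during surgeries performed with the DORC EVA device for comparison".

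Section 5.3 explains why preparation is thought to matter. It describes the set-up step, in which "the patients is draped while the vitrectomy device is being prepared", and adds "This whole procedure takes 10-20 minutes, depending on the complexity of" the case. It then notes that packaging has been reduced and the giving set simplified, and concludes: "This should shorten the total surgical time".

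Appendix B, the list of device issues in the surgical report and eCRF, has one surgical time field: "Device preparation time (HH:MM:SS". Its other entries record whether a given device problem occurred.

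**The concern.** The objective names one quantity and the parameter measures another. Preparation is at most one component of total surgical time. By the protocol's own account it runs alongside draping, so minutes saved in preparation need not all carry through to the total.

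The protocol also describes EVA Nexus features that act during the operation. Section 5.2 says a second infusion line removes the need to move the infusion midway through combined phaco-vitrectomy. Section 5.3 says the new infusion connection needs fewer surgical movements. Appendix B lists problems that could lengthen an operation, such as replacing a cassette or vitrectome. No operating duration is specified that would show the net effect of these.

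At stake is what may be concluded under this objective. A shorter preparation time, read against the objective as worded, could be taken as evidence of shorter surgery when the total was not measured.

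**Working it through.** The plan gives no figure for preparation or total time that could be reproduced as an effect size or precision statement. The sample size of 250 in section 8.1 was set to obtain at least 10 complications and has no bearing on time. The check is mainly a reading of every place where a duration could be specified.

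**1. Where a duration could appear**

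| Place | Time specified |
|---|---|
| Section 6, row for this objective | Device preparation time, EVA Nexus and concurrent DORC EVA |
| Section 6, primary parameters, and section 11.1 | None: indication, phaco power, dyes, laser, tamponade |
| Section 6, third secondary objective ("The surgical parameters include a range of data collected on the following") | None named: ten device-function headings without variables |
| Section 7.2 flowchart | None: a surgical summary is listed without contents |
| Appendix B | Device preparation time |
| Appendices C and D | Dates of adverse events; dates and, where known, times of device deficiencies |

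Appendix D could give the duration of an individual deficiency, but not the duration of the operation. Nowhere does *total surgical time* have a defined start or end point.

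**2. How a preparation saving reaches the total**

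Let P be preparation time, D draping time and O the time from readiness to the end of surgery. If draping and preparation start together and surgery begins when both are done, then

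T = max(P, D) + O.

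With D and O the same for both devices, and preparation falling from P0 to P1 = P0 − x, the total saving is max(P0, D) − max(P1, D):

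- D ≤ P1: saving = x
- P1 < D < P0: saving = P0 − D, which is less than x
- D ≥ P0: saving = 0

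Illustration with assumed values inside the 10–20 minutes of section 5.3, P0 = 15 and P1 = 10, so x = 5. The total saving is 5 minutes if D ≤ 10, 15 − D if D lies between 10 and 15, and 0 if D ≥ 15. D is not given and not recorded, so the data cannot place the answer in that range. If O also differs between devices, the true difference in T can lie outside 0 to 5 minutes in either direction.

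The 10–20 minutes is itself uncertain as an input. The text does not make clear whether it includes draping, and the form in Appendix B displays 00:04:15. That entry may be only a form example and is not used here.

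**3. Why a clear preparation result does not carry over**

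The documents give no standard deviation, so these values are assumptions. For a difference d in means at two-sided 5% and 80% power, n per group = 2(1.96 + 0.84)²SD²/d², computed with unrounded normal quantiles.

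| Assumed saving d | SD 3–5 min (assumed for preparation) | SD 15–30 min (assumed for total) |
|---|---|---|
| 5 min | 6 to 16 per group | 142 to 566 per group |
| 2 min | 36 to 99 per group | 883 to 3,532 per group |

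On these assumptions a number of cases that settles preparation time could leave total time open even if it were measured.

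**4. The planned comparison**

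Section 6 intends an EVA Nexus versus DORC EVA comparison of preparation time. Sections 13.1 and 14.5, however, describe secondary analyses only as patients with complications versus patients without. No between-device analysis of any time is set out, and no number of concurrent DORC EVA cases is given.

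**The case against.** The strongest reply is that nothing is hidden. Section 6 defines the measure beside the objective, section 5.3 words the link to total time as an expectation, and this is one of three secondary objectives with no hypothesis or sample-size claim attached. On that view the point is one of wording. Much of this stands: rewording is the simplest remedy, and preparation time is worth reporting in its own right. It does not remove the mismatch, because the objective as written asks about a quantity that the specified parameter does not measure.

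Three stronger readings are tempting, and the documents do not support them.

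- A reader might infer that no other time is recorded at all. Appendix B is only part of the surgical report, the surgical summary in section 7.2 is not itemised, and the device-function headings in section 6 name no variables. What can be said is that no operating or total time is *specified*.
- A reader might infer that changes in the operating phase go wholly uncaptured. Appendix B records the occurrence of device error messages and cassette replacements, and section 6 compares such issues with historical DORC EVA data. Appendix B does not record the time they cost.
- A reader might infer that a preparation saving leaves the total unchanged. That needs draping to last at least as long as preparation, and no draping time is given. The supportable statement is that the total may fall by less than x.

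Nor do the documents say that a shorter preparation time will be reported as shorter surgery. That is a risk left open by the wording, not a stated plan.

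**Conclusion.** The point holds for this objective. As planned, the data can support a conclusion on device preparation time but not on total surgical time. The specified parameter is a different quantity from the one in the objective, and the step from one to the other is assumed.

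The size cannot be fixed from the documents. With operating time unchanged, a preparation saving of x minutes corresponds to a total saving between 0 and x. This rests on reading section 5.3 as parallel draping and preparation, and on counting preparation as part of surgical time, which the plan does not define. The 15-to-10-minute example and the standard deviations are assumptions.

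The primary safety endpoint and the other two secondary objectives are not affected. The change is worth making because it is specific, cheap, and alters what the trial may conclude.

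**What to change.** **Preferred.** Reword the objective in section 6 to *device preparation time, EVA Nexus versus concurrent DORC EVA*. In section 5.3, present the statement on total time as an expectation that this study does not test. Draw no conclusion on total surgical time in the report. Add the between-device comparison of preparation time to sections 13.1 and 14.5. The cost is a few sentences and no new data.

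**Alternative, if total time is wanted.** First establish whether the hospital's surgical records already hold start and end times. The documents do not say, so this is an assumption. If they do, define total surgical time by explicit start and end points and extract it for EVA Nexus and for the concurrent DORC EVA cases already being timed. Compare the devices by procedure type (cataract, vitrectomy, combined), and keep preparation time as a component. Report the differences descriptively with confidence intervals, because the devices are not randomised and case mix may differ even within a procedure type. State how many DORC EVA cases there will be and how they are chosen. This costs two extra fields per case plus extraction. On the assumed standard deviations above, it may still not resolve a saving of a few minutes.

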-Flow pumps displace a required amount of fluid, and only build up vacuum secondary to this fluid displacement. In conditions with low resistance, there is little or no vacuum-buildup. Most flow pumps are less powerful than vacuum pumps, but can provide a better control of the flow. This increases safety when working close to the retina.

A typical example of a flow pump system is a peristaltic pump. Although such pump is popular in cataract surgery, it is only used for vitrectomy surgery in conjunction with a vacuum pump.

Our present vitrectomy machine in the UZLeuven (DORC EVA) has a piston-pump which can be steered to perform as a vacuum system or as a flow system. This unique feature allows the surgeon to choose the best suitable mode for each individual step of the surgery.

3. Infusion system.

Since vitreous is removed from the eye, an infusion system must be present to maintain the eye pressure. There are two infusion systems used for vitrectomy surgery:

-Gravity system: the infusion bottle (or bag) is suspended on a telescopic infusion pole.

The pole can be extended using the vitrectomy machine to a higher or lower height, which increases the pressure at which the infusion liquid is driven towards the eye. The disadvantage of such system is that the infusion pole movement has its speed limits, which can be a problem when a fast pressure change is required in the eye (such as in case of hemorrhage).

-Air system: using a spike, air is blown into the infusion bottle. A higher air pressure will increase the force at which liquid is driving towards the eye. Such system can respond more quickly to required pressure changes. Our present vitrectomy machine in the UZLeuven (DORC EVA) has this type of infusion system.

A logistical side-effect of such air-driven system is that the infusion liquid connected to the eye must be packaged in glass bottles, since plastic bags or plastic bottles have an inherent flexibility which would cause unwanted hysteresis.

-In case of combined phaco-vitrectomy, both infusion in the anterior and in the posterior eye segment is required. Since our present vitrectomy device (DORC EVA) only has a single infusion line, the tubing needs to be reconnected from the phaco handpiece on the posterior segment infusion canula halfway the surgery.

4. Light.

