The EVA Nexus system has an active infusion system, which constantly provides a stable infusion to the eye and a stable intra-ocular pressure during surgery. Hence, it features automated control of the intra-ocular pressure during anterior and posterior segment surgery.

The fixed and gravity modes are both pressure controlled and can be regarded similar technology with the same functional result. The eIOP mode in EVA NEXUS supports the surgeon to maintain the IOP by maintaining the Irrigation/Aspiration balance (regulated by the pump system to get precise Intra Ocular Pressure control), where in EVA Intra Ocular Pressure is a result of the surgeon controlled settings of the system.

The EVA Nexus has twin irrigation lines, which omits the need to switch the infusion halfway the surgery in case of combined phaco-vitrectomy

Another, logistical implication is that the infusion liquid used during cataract surgery or vitrectomy surgery must not be packaged anymore in a glass bottle, since the DORC EVA Nexus actively aspirates the infusion liquid from the container. Therefore, less expensive packages of infusion liquid can be used (fluid bags or plastic bottles).

5. Light

The system had a LED-powered light source, with filtered output to eliminate the shorter light wavelengths that induce light toxicity during prolonged exposure to the retina. This is the same light source as in the present DORC EVA device.

6. Phaco ultrasound

The phaco handpiece that fits to EVA Nexus is the same CE-labeled commercial handpiece already used on our present surgical device.

Although the design is somewhat different, both EVA and EVA NEXUS use similar principles of operation to drive the phaco handpiece for emulsification or fragmentation of the lens. All performance requirements are the same.

7. Laser module

The EVA Nexus has a built-in 532 nm diode-laser. This is the same laser module as used in our present vitrectomy device.

8. Silicone oil injection (VFI).

There are no differences between the EVA and EVA NEXUS for silicone oil injection.

9. Silicone oil extraction.

There are no differences between the EVA and EVA NEXUS for silicone oil extraction.

10. Micro Injection

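### The objective is total surgical time, but only preparation is timed, so in combined phaco-vitrectomy the DORC EVA's mid-surgery infusion reconnection is left out

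*Combined protocol and SAP*

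**What the plan says.** The secondary objectives table in section 6 gives the aim as "To evaluate the possible reduction of total surgical time". The parameter listed against it is preparation time: "The time that was required to prepare the EVA Nexus will be recorded (connecting of supplies + priming"). For the comparator it adds: "During the study period, this time will also be recorded during surgeries performed with the DORC EVA device for comparison". In the Appendix B list, device preparation time is the only duration field.

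Section 5.3 describes what preparation consists of: "This involves connecting of all the surgical supplies (see above) and priming of the device". It puts the whole procedure at 10-20 minutes, depending on how complex the case is.

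Two passages describe infusion in combined phaco-vitrectomy. For the DORC EVA, which has a single infusion line, section 5.1 says "the tubing needs to be reconnected from the phaco handpiece on the posterior segment infusion canula halfway the surgery". For the new machine, section 5.2 says "The EVA Nexus has twin irrigation lines, which omits the need to switch the infusion halfway the surgery in case of combined phaco-vitrectomy".

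Sections 8.2 and 11.3 show that the population mixes vitrectomy, cataract and combined surgery. Most vitrectomies in phakic patients over 50 are expected to be combined.

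**The concern.** The protocol names the removal of the infusion switch as one of the improvements of the new platform. The switch happens during the operation, so it belongs to total surgical time. The recorded interval ends when priming ends, so it cannot register the switch on the DORC EVA or its absence on the Nexus.

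The objective and the parameter therefore differ in exactly the cases where the two infusion designs differ. A result on preparation time could be reported as an answer about total surgical time, although a known difference between the machines was never measured. If the preparation difference is small, a real saving in combined surgery could be missed.

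**Working it through.** The plan gives no effect size, standard deviation or sample size for preparation time, so there is no figure of its own to reproduce. The check is an accounting of what the interval contains, followed by an illustration of size.

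**What the clock covers**

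| Step | DORC EVA | EVA Nexus |
|---|---|---|
| Connecting supplies and priming (sections 5.3, 6) | timed | timed |
| Infusion switch in combined surgery (sections 5.1, 5.2) | takes place mid-surgery, not timed | not needed |
| Infusion switch in vitrectomy-only or cataract-only surgery | none described | none described |

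The gap is confined to combined phaco-vitrectomy.

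**Inputs**
- Preparation time: 10-20 min (section 5.3).
- Duration of the DORC EVA switch, s: not given; assumed 0.5-2 min.
- Share of surgeries that are combined, p: no percentage given; assumed 30-60%, since section 11.3 says only that most phakic vitrectomy patients over 50 have combined surgery.

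**Size of the omission**
- Average per surgery = p × s.
- Low: 0.3 × 0.5 = 0.15 min; 0.15/20 = 0.75%, about 1%.
- High: 0.6 × 2 = 1.2 min; 1.2/10 = 12%.
- Within combined surgery (p = 1): 0.5 to 2 min, that is 0.5/20 = 2.5% to 2/10 = 20%.

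These figures treat the whole switch as saved. If attaching the second Nexus line also takes time during the operation, the net omission is smaller.

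**Comparison with case mix**

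The plan does not say how surgeries are allocated to one machine or the other. Take 10 and 20 min as the times for simple and complex cases. A 10-percentage-point difference between machines in the share of complex cases then shifts the mean difference by 0.10 × (20 − 10) = 1.0 min, in either direction. That is close to the top of the 0.15-1.2 min range, so the omission alone does not fix the sign of the overall error.

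**Planned analysis**

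Sections 13.1 and 14.5 compare secondary-objective data between patients with and without complications. Neither specifies a Nexus-versus-DORC EVA comparison of time, nor a breakdown by surgery type.

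**The case against.** The strongest reply is that both machines are timed on the same nominal interval, so the comparison is like with like. For a claim about preparation time alone this is right. If a second line did lengthen Nexus preparation, that would be a true difference in preparation time and not a bias. The reply does not rescue the objective as written, which is about total surgical time.

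Three stronger readings are tempting, and the documents do not carry them:

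- A reader might infer that the second Nexus line is connected and primed inside the timed set-up, so that one task is counted on one machine and not on the other. This is plausible, because preparation covers all supplies, but no section says when that line is connected. Attachment to the cannula may well be intra-operative on both machines. Moving tubing mid-surgery and readying an extra line are also different tasks.
- A reader might conclude that the comparison is biased against the Nexus overall. Section 5.3 also says that "the infusion giving set has been simplified significantly for the EVA Nexus platform", a simplification that plausibly shortens connecting and priming and so counts inside the timed interval. Device allocation and case mix are uncontrolled and can push either way.
- A reader might add the packaging change: "The packaging of the surgical supplies was reworked (reduction in the amount of packaging materials"). Whether unpacking falls inside the interval is not settled, because no start point is defined. If it is left out, it is left out on both machines. It is therefore not counted in the size above, but it is a reason to define the start point.

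**Conclusion.** The point stands in limited form. In combined phaco-vitrectomy, preparation time is an incomplete proxy for total surgical time, because it omits a DORC EVA step that the Nexus design removes. That component taken alone disfavours the Nexus; the net direction of bias is not established. Vitrectomy-only and cataract-only surgeries are not affected by this omission.

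The size rests entirely on the assumed switch time and share of combined cases: 0.15-1.2 min per surgery on average. The low end is negligible. The high end could matter for a comparison on a 10-20 min scale. This is a secondary objective and does not touch the primary safety endpoint, but the mismatch is simple to remove before data are collected.

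**What to change.** 1. In section 6 and in the Appendix B time field, define the same start and stop points for preparation on both machines, and state whether unpacking is included. The Appendix B screenshot shows an example entry of 00:04:15 for the Nexus, against the 10-20 min in section 5.3. It is only an example, but it shows why the boundaries need stating.
2. In combined surgery, record on both machines the intra-operative time spent connecting or switching the infusion, or record total surgical time on both. Timing the step on the DORC EVA alone would create a new asymmetry in favour of the Nexus.
3. In sections 13.1 and 14.5, specify the Nexus minus DORC EVA difference, reported separately for vitrectomy-only, cataract-only and combined surgery, with preparation time alone as a supporting figure.
4. If the intra-operative time is not recorded, limit the conclusion to preparation time and state the omission for combined surgery.

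The cost is a reworded definition, a short addition to the analysis text and one extra time field in combined cases. No visit or examination is added.
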